1.1 Sample size calculation

For the time to event outcome, use the median reoccurrence time of similar populations in the literature to estimate the hazard ratio (HR). The median reoccurrence time described in the literature is 18 months. If we do not want to miss the 6-month improvement in event time in the treatment group, then HR estimates the risk ratio of reoccurrence time at 18 months in the control group and 24 months in the treatment group.

Risk ratio=(risk rate of treatment group)/(risk rate of control group)

Risk rate=1/(median recurrence time)

Therefore, the risk ratio can be estimated as: Risk ratio=(1/24)/(1/18)=18/24=0.75

The estimated risk ratio is 0.75, which represents a 25% reduction in risk effect for the treatment group compared to the control group. The sample size is based on the parallel design of the superiority program, survival endpoint, 90% efficacy, 0.05 significance level, bilateral significance level, HR 0.75. Using PASS11 software, it is estimated that each group requires 635 cases, and an increase of 10% would result in 700 cases per group. Therefore, the planned total sample size is 1400 patients with lung cancer.

2、 Case selection

In this experiment, qualified participants will be recruited from each center, as the annual number of lung surgeries in each center reaches around 8000 cases.

Inclusion Criteria

1. Age range: 18-80 years old.
2. Electively undergo minimally invasive (thoracoscopic or robotic) surgery for clinical stage I and II lung cancer.
3. Willing and capable of providing consent.

Exclusion criteria

1. Palliative surgery without intention of cure.

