2. ASA IV
3. Patients who are known or suspected to be allergic to lidocaine.
4. Patients who are currently pregnant or breastfeeding.
5. According to the Summary of Lidocaine Product Characteristics, patients who may experience adverse reactions due to accumulation of lidocaine intravenous infusion.
6. The current liver function is abnormal, with ALT or AST exceeding the laboratory reference range by 2 times.
7. Currently severe renal insufficiency (blood creatinine $\geq 451\text{umol/L}$ or glomerular filtration rate (calculated by MDRD formula) $<30\text{ml/min}$).
8. Epilepsy.
9. Cardiac conduction abnormalities, including second or third degree heart block without a pacemaker, left bundle branch block, sick sinus syndrome, and pre excitation syndrome (confirmed by

electrocardiogram based on medical history), as well as patients in a low cardiac output state with currently reduced left ventricular ejection fraction.

10. Concurrent use with continuous infusion of other local anesthetics (such as epidural).
11. Patients who use drugs that may cause exclusion reasons, including Class I and III antiarrhythmic drugs (such as metoprolol, amiodarone), cimetidine, and antiviral drugs. Qualifications will be determined by local clinical doctors and verified by clinical trial doctors.
12. Patients weighing less than 40kg

Termination criteria for the study (subjects experiencing conditions that make it inappropriate to continue the study, including worsening of the condition, serious adverse events, poor compliance, etc.)

Research methods

1. Intervention measures

Research drug (IMP)

2% lidocaine hydrochloride injection for infusion, prepared as a 50mL syringe and continuously pumped for administration.

Placebo

0.9% sodium chloride solution for infusion, prepared into a 50mL syringe and continuously pumped for administration.

2. Dose plan

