Lidocaine is administered intravenously at an ideal body weight (IBW) of 1.5 mg/kg starting from anesthesia induction, for 10-20 minutes, and then continuously infused at 1-1.5 mg/kg/h until 12 hours after returning to the ward, with a maximum rate of 120 mg/h. Use ideal weight instead of actual weight to prevent toxicity in very overweight patients. In patients with a weight lower than the ideal weight, the actual weight should be used to calculate the dose. The patient needs to be admitted to a highly dependent ward or equivalent facility for continuous cardiac monitoring during lidocaine infusion. Patients in the placebo group had the same infusion rate as those in the treatment group.

Example

IBW (Kg) initial dose (1.5 mg/kg) infusion rate (1.5 mg/kg/h)

40 3ml (10-20min) 1-3ml/h

50 3.75ml (10-20min) 1.25-3.75 ml/h

60 4.5ml (10-20min) 1.5-4.5 ml/h

70 5.25ml (10-20min) 1.75-5.25 ml/h

80 and above 6 ml (20 minutes) 2-6 ml/h

Table 1: Dose Guidelines Based on IBW (Broca Index): Male: Height (cm) -100; Female: Height (cm) -105. Attention: For patients with a weight lower than the ideal weight, the actual weight should be used to calculate the dosage.

Therefore, for the placebo/saline group, if the IBW is 70kg, the patient will receive an initial infusion of 0.9% sodium chloride at 5.25ml over 10-20 minutes, followed by an infusion at 1.75-5.25ml/h.

3. Dose adjustment

Dose changes are not allowed in this study. If the supervising medical professional suspects acute systemic local anesthetic toxicity symptoms, the infusion must be stopped and not continued. In this case, supportive treatment and lipid rescue will be provided. The discussion on the possible adverse events caused by lidocaine toxicity is as follows. If the infusion is interrupted due to issues such as infusion pump failure, catheter failure, or accidental disconnection, the infusion can be restarted at the original rate and the event recorded.

4. Additional care and procedures

To reduce the possibility of confounding factors, general anesthesia should be maintained under a combination of intravenous and inhalation anesthesia. Postoperative care follows the unit's standard to enhance postoperative rehabilitation protocol. The pain control program will be consistent with the unit's standard procedure. However, during IMP infusion, simultaneous continuous infusion of other local anesthetic drugs (such as epidural or wound catheters) cannot be performed.

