Lidocaine can inhibit cancer cell proliferation at doses that have minimal impact on normal cells. The infusion dose and duration selected

in this study are within the recommended range of the latest international consensus statement on the safe use of intravenous lidocaine infusion. Lidocaine should be administered intravenously at an initial dose of no more than 1.5mg/kg of ideal body weight, with an initial infusion time of at least 10 minutes. During the maintenance period, the infusion rate of 1.5mg/kg/h should not exceed 24 hours, and the maximum infusion rate should not exceed 120mg/h. The above medication should be calculated based on ideal body weight. If the actual body weight is lower than the ideal body weight, it should be calculated based on the actual body weight. When toxicity occurs, according to the guidelines of the British and Irish Society of Anesthesiologists, lidocaine infusion can be temporarily suspended and treatment can be carried out using readily available 20% intravenous lipids in the operating room and intensive care unit.

9. Quality Control and Quality Assurance in Research

Strictly follow relevant SOPs during the clinical research process, conduct unified training before the implementation of the study, and monitor IMP/placebo infusion as part of the standard care for patients. Due to the infusion of IMP/placebo from the start of surgery until 12 hours after returning to the ward, all participants were hospitalized during the infusion period. The infusion rate table will be provided to the research team to minimize user errors during administration. The data

will be collected at the hospital during routine hospital appointments and postoperative recovery periods. We will strive to collect outcome data from all randomly assigned participants, regardless of whether they received IV lidocaine/placebo. Communicate with the surgeon and strictly follow the diagnosis and treatment plan according to the protocol. Strictly develop a follow-up plan form. The data is recorded using Redcap software.

10. Statistics process

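### Section 8 allows a temporary suspension of the lidocaine infusion when toxicity occurs, while section 3 requires a permanent stop on suspicion (minor)

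*Protocol*

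**What the plan says.** Section 3 (Dose adjustment) sets the rule for handling the study drug: "If the supervising medical professional suspects acute systemic local anesthetic toxicity symptoms, the infusion must be stopped and not continued". It adds supportive treatment and lipid rescue, and then points the reader onward: "The discussion on the possible adverse events caused by lidocaine toxicity is as follows". The same paragraph contains the only restart permission in the protocol, which reads in part: "interrupted due to issues such as infusion pump failure, catheter failure, or accidental disconnection, the infusion can be restarted at the original rate".

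Section 8 (Observation of adverse events) is mainly a justification of dose and duration, with ceilings for the bolus and the maintenance rate. Its last sentence turns to management: "When toxicity occurs, according to the guidelines of the British and Irish Society of Anesthesiologists, lidocaine infusion can be temporarily suspended". It goes on to say that 20% intravenous lipid can be given.

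Two other places touch the subject. Section 2 (Dose plan) states: "The patient needs to be admitted to a highly dependent ward or equivalent facility for continuous cardiac monitoring during lidocaine infusion". The termination criteria, placed after the exclusion criteria, refer to "conditions that make it inappropriate to continue the study, including worsening of the condition, serious adverse events".

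**The concern.** For one event, lidocaine toxicity during the infusion, the protocol gives two instructions that cannot both be followed to the letter. An infusion that must not be continued cannot also be one that is only temporarily suspended.

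What is at stake is participant safety and clarity of conduct. Section 2 has the infusion run on for 12 hours after the patient is back on the ward, so the decision to stop or resume can arise there as well as in theatre. A clinician who follows section 3 breaches nothing. One who relies on section 8 could treat the stop as optional or provisional. If an infusion were resumed after toxicity, section 3 would make that a deviation, while section 8 would give an argument that it was not.

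**Working it through.** No arithmetic applies. The check sets the two instructions side by side.

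| Feature | Section 3, Dose adjustment | Section 8, Observation of adverse events |
|---|---|---|
| Trigger | Suspected acute systemic toxicity | Toxicity that has occurred |
| Obligation | Mandatory (*must*) | Permissive (*can*) |
| Duration of the stop | Permanent | Temporary |
| Accompanying treatment | Supportive care and lipid rescue | 20% intravenous lipid |
| Restart condition or rate after toxicity | None; continuation is barred | None stated |
| Source | The protocol's own rule | An outside guideline |

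1. *Same event?* Yes. Both concern toxicity from the study infusion, and both call for lipid treatment.

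2. *Could the two form a graded scheme?* No. The stricter response is tied to the lower threshold (suspicion) and the laxer one to toxicity that has actually occurred. A sensible scale would run the other way.

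3. *Is either sentence superseded?* No. Both stand in the body of the protocol, and neither belongs to an amendment log.

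4. *Does any text set precedence?* No. Section 3 refers forward to a discussion of toxicity, and section 8 is the only later text on managing it. A reader who follows that pointer arrives at the weaker wording.

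5. *Does other text settle the matter?* The termination criteria concern whether a subject continues in the study, not whether a pump is restarted. Continuous cardiac monitoring helps to detect toxicity but does not say what to do with the infusion afterwards.

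6. *Does section 8 grant a restart?* Not in terms. It states no condition, timing or rate. The implication rests on two words: *can*, which makes even the stop discretionary, and *temporarily*, which supposes an end to the suspension.

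**The case against.** The best defence is that the operative rule is already clear. Section 3 governs the handling of study drug, is mandatory, bars dose changes, and acts at first suspicion. A clinician who obeys it has stopped for good before the section 8 sentence comes into play. Section 8 is mostly rationale, and its sentence reports an outside guideline. Section 3 itself calls the later text a discussion, which suggests explanation and not a rival rule. Section 9 adds SOPs, unified training and an infusion rate table. The English is also loose elsewhere (section 1.1 writes efficacy where power is meant, and section 10 writes truncated where censored is meant), so *temporarily suspended* may simply be a poor rendering of *stopped*.

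Most of this stands, and it is why the point is minor. It does not remove the conflict. Section 8 offers the guideline as the way to act when toxicity occurs and does not say that the trial departs from it. Training has to teach one rule, and the protocol supplies two. Loose translation cannot be verified from the text, and the remedy would be the same.

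Three stronger readings are tempting, and the document supports none of them.

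- *That section 8 authorises a restart after toxicity.* It states none, so no additional lidocaine dose can be attributed to the wording.
- *That the restart permission in section 3 extends to toxicity because its list is introduced by* such as. All three examples are technical failures, and the bar on continuing after suspected toxicity stands in the same paragraph.
- *That the whole lidocaine group is affected.* The sample size section says "an increase of 10% would result in 700 cases per group", but that is the size of the arm. The wording matters only for patients in whom toxicity is suspected.

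**Conclusion.** The contradiction is real as the text is written: section 8 is permissive and provisional where section 3 is mandatory and final, and no text says which prevails. Section 3 holds the specific and safer rule, so section 8 is the place to correct.

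Severity is minor. The number of patients concerned cannot be estimated, because the protocol gives no toxicity rate, and no harm can be quantified. Sample size and primary analysis are unaffected. The conclusion rests only on the two sentences and on the ordinary meaning of *temporarily*. It assumes nothing about what the cited guideline says, which cannot be checked from the protocol.

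**What to change.** In the last sentence of section 8, replace the words that permit a temporary suspension with *must be stopped and not restarted*, and keep the 20% intravenous lipid treatment. Section 8 then agrees with section 3. No edit to section 3 is needed, because its restart permission already sits beside the bar on continuing after suspected toxicity.

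Since the section 8 sentence attributes its instruction to a guideline, the sponsor should check that the attribution still reads correctly after the change.

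The cost is one phrase, with no change to design, sample size or analysis. It is best made before recruitment, which is planned from January 2026, or by amendment if recruitment has begun.

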Cancer staging is indeed associated with recurrence, especially when cancer cells migrate from the primary site. Stage I ground glass nodules, even if the pathological type is invasive adenocarcinoma and larger than 3cm, still have a 5-year 100% survival rate. Stage III and IV lung cancer, due to the invasive spread of cancer, surgery is usually not for cure, but mainly for symptom relief, and lidocaine is unlikely to provide benefits. Stage I solid nodular lung cancer involves vascular and pleural invasion, while stage II involves vascular and lymphatic system invasion, requiring extensive surgical resection [12]. These patients may benefit the most from lidocaine and will be the main target of this study. We will recruit patients with all cancer stages to understand potential differences in

response to lidocaine treatment.

Lidocaine has an inhibitory effect on tumor cells, which is mostly based on animal studies, and toxic doses are often used in animal studies. There are few high-quality studies in clinical practice. This study aims to explore whether lidocaine infusion at a safe dose can bring the value of prolonging survival for lung cancer patients after surgery, which is of great significance.

Research objective

1. Main objective: To evaluate the effect of perioperative lidocaine infusion on postoperative reoccurrence and metastasis in patients with non-small cell lung cancer.
2. Secondary objective: To explore the value of perioperative lidocaine infusion in prolonging the survival of patients with non-small cell lung cancer

Research design types, principles, and experimental procedures

1. Research Design

This is a 1:1 parallel double-blind (patient and data collector blinded, prepared by anesthesia nurses and administered by anesthesiologists) randomized controlled trial comparing the efficacy of intravenous infusion of lidocaine versus placebo/saline during minimally invasive (thoracoscopic or robotic) surgery in lung cancer patients.

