5. Postoperative analgesia management

To reduce the possibility of confounding factors, general

anesthesia should be maintained under a combination of intravenous and inhalation anesthesia. Postoperative care follows the unit's standard to enhance postoperative rehabilitation protocol. The pain control program will be consistent with the unit's standard procedure. However, during IMP infusion, simultaneous continuous infusion of other local anesthetic drugs (such as epidural or wound catheters) cannot be performed. After the surgery, all patients were uniformly treated with sufentanil 2ug/kg diluted to 100ml and pumped with 2ml/h for intravenous analgesia

6. Randomization

After obtaining consent, participants will be randomly assigned (1:1) to receive intravenous lidocaine or placebo using a minimization algorithm. The minimum criteria include age (<45 years, 45-65 years, 65-80 years), gender, trial center.

6. Observation project

Main outcome measure

Assess the reoccurrence time of lung cancer patients within 36 months from the date of surgery.

Secondary outcome measure

1. Disease free survival (DFS)
2. Objective remission rate of patients' diseases
3. Health related Quality of Life Questionnaire EQ-5D-5L
4. Cancer specific quality of life measured using the Functional

Assessment of Cancer Therapy (FACT-L) questionnaire.

Other observation indicators

1. The total length of hospital stay, including readmission, is 36 months.
2. Changes in pro-inflammatory cytokine levels (IL-6, TNG - α) from baseline on the third day after treatment and upon discharge.

On the 1st and 3rd day after treatment and at discharge, changes in reticular fiber dissolution markers (matrix metalloproteinases MMP-9, MMP-2) from baseline were observed.

3. Perioperative nausea, vomiting, delirium, pain control, and incidence of cardiovascular accidents 6 and 12 months after treatment completion.

7. Efficacy evaluation criteria

Follow up chest CT scans at 6, 12, 18, 24, and 36 months after surgery were conducted to evaluate whether lung cancer patients had cancer reoccurrence and the time of reoccurrence within 36 months from the date of surgery. And evaluate the cancer specific quality of life using the lung cancer treatment function assessment questionnaire for patients. The shortened recurrence time and improved specific quality of life indicate therapeutic efficacy.

8. Observation of adverse events

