Statistics will be recorded and managed using Redcap data, and analyzed using SPSS21 software. The analysis will be conducted according to the intention to treat principle. The statistical analysis plan for this study includes summarizing baseline data, conducting primary outcome analysis using time to event analysis, and conducting additional survival analysis. Baseline variables such as age group, gender, comorbidities, ASA classification, cancer stage, cancer TNM classification, pathological type, neoadjuvant targeted therapy, radiotherapy, and chemotherapy will be summarized using appropriate descriptive statistical methods, using mean and standard deviation or median and quartile range (depending on the applicability of continuous variables). The categorical variables will be summarized using the frequency and percentage of participants in each category. Researchers will use EDC to fill out CRF. The data will be stored on a secure server.

The source documents of CRF report information will be archived in the center and available for monitoring, IRB/IEC review, and regulatory inspection as needed. According to applicable regulations, researchers must retain all research records/documents.

The main outcome is defined as the time of cancer reoccurrence within 36 months after surgery in patients with stage I and II lung cancer. Multiple Cox regression models will be used to analyze the main results and adjust the truncated data. The truncated data includes participants who have not experienced recurrence or death within 36 months, as well as those who have been lost to follow-up or withdrawn from the study.

The risk ratio will be estimated by comparing the risk rates of the placebo group and the lidocaine group, taking into account the truncated data of the participants and adjusting for covariates. In addition, Kaplan Meier plots will be used to visualize and compare survival distributions, while Log rank tests will evaluate the differences between the two groups.

We will use the study drug allocation ($x=0$ placebo, $x=1$ lidocaine) as the independent variable, the time of cancer recurrence or death as the dependent variable, and age group (<45, 45-65, 65-80), gender, number of comorbidities, ASA classification, cancer staging, neoadjuvant radiotherapy, and chemotherapy as adjusted covariates.

Clean the experimental data and construct an analysis dataset suitable for statistical analysis. Data quality control is achieved through the accuracy

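### The primary endpoint is defined and sized as time to recurrence, but the only specified Cox model and the censoring rule count death as an event

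*Protocol*

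**What the plan says.** Four places in the protocol point to recurrence alone:

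- **Research objective**, main objective: "To evaluate the effect of perioperative lidocaine infusion on postoperative reoccurrence and metastasis in patients with non-small cell lung cancer". Survival is the separate, secondary objective.
- **1.1 Sample size calculation**: "The median reoccurrence time described in the literature is 18 months". This is set against 24 months on lidocaine to give HR 0.75. No death rate enters.
- **6. Observation project**, main outcome measure: "Assess the reoccurrence time of lung cancer patients within 36 months from the date of surgery".
- **10. Statistics process**: "The main outcome is defined as the time of cancer reoccurrence within 36 months after surgery".

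Two statements in section 10 point to recurrence or death:

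- The censoring rule: "The truncated data includes participants who have not experienced recurrence or death within 36 months", together with those lost to follow-up or withdrawn.
- The only model written out, which takes "the time of cancer recurrence or death as the dependent variable".

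Section 6 also lists disease-free survival (DFS) as the first secondary outcome, apart from the primary.

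**The concern.** The outcome and the model that tests it use different events. A patient who dies without recurrence has no event under the definition but has one under the model. Three things follow.

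- The test that would be run is not of the endpoint that was defined and powered.
- The two definitions can give different results, and the protocol does not say which is primary. A mid-term analysis is scheduled for 2027 (Research time), so outcome data may be seen before the choice is settled.
- If DFS has its usual meaning of recurrence or death, the primary model duplicates the first secondary outcome and recurrence itself has no specified model.

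If lidocaine does not affect deaths without recurrence, counting them pulls the HR towards 1.

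**Working it through.** **Reading the text.** The censoring rule comes directly after the sentence assigning Cox regression to the main results. The censored are those with neither recurrence nor death by 36 months, plus those lost or withdrawn. A patient who dies without recurrence is in neither group, so the death is an event. The model sentence says the same directly. No recurrence-only model appears, and the Kaplan-Meier and log-rank sentence gives no event definition that would settle the matter.

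**The plan's own figures.** HR = (1/24)/(1/18) = 18/24 = 0.75, as stated. For 90% power at two-sided 0.05 with 1:1 allocation, the Schoenfeld formula gives

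4 × (1.960 + 1.2816)² / (ln 0.75)² = 4 × 10.507 / 0.08276 = 508 events.

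The stated 635 per group (1,270 in all) then implies an event probability of 508/1,270 = 0.40. The protocol does not state this probability. With 36 months' follow-up at the stated medians it would be (0.75 + 0.646)/2 = 0.698. The 635 therefore depends on unstated follow-up assumptions, but the present point does not depend on how it was reached.

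**Effect of counting deaths (illustration).** Let q be the share of the control composite hazard that is death without recurrence. The document gives no value, so 5%, 10%, 20% and 30% are assumptions. Such deaths are assumed equally frequent in both arms.

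- Recurrence hazards: ln 2/18 and ln 2/24 per month. Death hazard in both arms: (ln 2/18) × q/(1 − q).
- Composite HR = 0.75(1 − q) + q. For q = 20%: 0.60 + 0.20 = 0.80.
- Events for 90% power = 4 × 10.507/(ln HR)². For HR 0.80: 42.03/0.04979 = 844.1, rounded up to 845.
- Power = Φ(|ln HR| × √D/2 − 1.96), where D is the number of events.

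| q | Composite HR | Events for 90% power |
|---|---|---|
| 0 | 0.75 | 508 |
| 5% | 0.7625 | 572 |
| 10% | 0.775 | 647 |
| 20% | 0.80 | 845 |
| 30% | 0.825 | 1,136 |

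*Scenario A: 1,270 patients, each followed for 36 months.*

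| q | Composite events | Composite power | Recurrences | Recurrence-only power | Points lost |
|---|---|---|---|---|---|
| 5% | 914 | 98% | 861 | 99% | 0.4 |
| 10% | 941 | 97% | 834 | 99% | 1 |
| 20% | 999 | 94% | 775 | 98% | 4 |
| 30% | 1,058 | 88% | 708 | 97% | 9 |

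*Scenario B: the Research time calendar, read as even enrolment of 400, 600 and 400 patients over 2026, 2027 and January to October 2028, scaled to 1,270, with data cut-off at month 34.*

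| q | Composite events | Composite power | Recurrences | Recurrence-only power | Points lost |
|---|---|---|---|---|---|
| 5% | 518 | 87% | 489 | 89% | 2 |
| 10% | 541 | 84% | 479 | 88% | 4 |
| 20% | 589 | 77% | 458 | 87% | 10 |
| 30% | 645 | 69% | 432 | 85% | 16 |

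The last column of each table, taken from unrounded powers, isolates the effect of the event definition. The lower recurrence-only power in B comes from the shorter follow-up, which is a separate matter.

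**The case against.** The strongest objection is that the composite model need not be the primary one. Section 10 promises further survival analysis and speaks of several Cox models. The model sentence is not labelled primary and comes after the log-rank sentence. On that reading, though, the primary outcome would have no specified model, and the censoring rule, which is tied to the main results, would still treat death as an event. The contradiction remains.

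A second objection is that this belongs in the statistical analysis plan. A missing DFS definition could be left there, and is not the finding. Two incompatible event definitions cannot: an analysis plan could follow only one and would contradict the protocol on the other.

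Three criticisms stand in part.

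- Only two of the four recurrence statements formally define the outcome. The objective could be served by a composite, and how the literature source of the 18-month median treated deaths is unknown.
- The larger power losses need high death rates. Under the hazards above, shares of 20% and 30% mean about 16% and 26% of control patients dying without recurrence within 36 months. Nothing in the protocol supports such rates in resected stage I and II disease. Under full follow-up with few deaths, little power is lost.
- Scenario B rests on one reading of the calendar, and the protocol does not say what the mid-term analysis examines.

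**Conclusion.** The concern holds and must be fixed. The protocol is wrong as written: the endpoint that is defined and sized is time to recurrence, while the specified model and censoring rule analyse recurrence or death. This rests on the text alone.

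The consequence for power is conditional. If deaths without recurrence are unaffected by lidocaine and form 5% to 30% of the control hazard, the HR moves to between 0.7625 and 0.825. The event definition then costs about 0.4 to 9 points under full 36-month follow-up and about 2 to 16 points under the shorter calendar. Some deaths between CT visits may be cancer deaths with undetected recurrence, which would weaken the assumption of no effect. The severity rests on the ambiguity about what is being tested, not on a demonstrated shortfall in power.

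**What to change.** Choose one primary event definition and fix it before any outcome data are seen, including at the mid-term analysis.

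- **Option (a), recurrence only.** In section 10, change the dependent variable and the censoring rule. Treat death without recurrence as a competing event: a cause-specific Cox model and log-rank test with such deaths censored at the date of death, and cumulative-incidence curves. Define DFS as recurrence or death, as a distinct secondary outcome. Cost: wording and the analysis model.
- **Option (b), recurrence or death.** Change the main objective, the main outcome measure in section 6 and the definition in section 10. Restate the sample-size assumptions in 1.1 for the composite, with an explicit rate of death without recurrence. Kaplan-Meier and log-rank can stay. Replace the DFS secondary, which would then be a duplicate; overall survival is one candidate and would serve the secondary objective. Cost: wording and a restated sample-size basis. If that restatement shows too few events, more patients or longer follow-up would be needed.

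Neither change of definition needs extra visits, since the current model already requires dates of recurrence and of death as a first event. Overall survival, if adopted, would also need deaths after recurrence to be recorded.

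A minor separate correction: section 7, Efficacy evaluation criteria, states "The shortened recurrence time and improved specific quality of life indicate therapeutic efficacy". The direction is opposite to the 18-to-24-month assumption. It is probably a translation slip and no decision rule uses it, but it should read *prolonged*.
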